### **11.4. Reporting Procedures for Serious Adverse Events**

Reporting of all Serious Adverse Events will be done in accordance with the European Commission Guidelines on Medical Devices Serious Adverse Event Reporting (MEDDEV 2.7/3; December 2010).

SAEs/SADEs that pose an immediate risk to patient health or safety, will be reported to R&D immediately or no later than 24 hours after the Investigator is aware and to the device manufacturer, competent authority and the REC within 2 calendar days of the Chief Investigator becoming aware of the event.

All other reported SAEs/SADEs will be reported to R&D and competent authority within 7 calendar days of notification, if appropriate. This will not include SAEs that may be expected as part of the risks of routine care. Adverse device events (SADEs, USADEs) and device deficiencies will also be reported to the device manufacturer. All SAEs will be followed up to resolution.

SAEs/SADEs will be considered as any adverse event occurring from the injection of Sienna+ tracer during endoscopy to patient's discharge from hospital following their scheduled surgery.

### **11.5. Expectedness**

Expectedness will be determined according to the Manufacturers risk analysis report.

Expected adverse reactions are uncommon but may include hypersensitivity reaction such as rash, itching, dizziness and lightheadedness. If inadvertent injection into the vascular system occurs anaphylactic reaction is possible. There may be brownish discolouration of the tissue around the injection site that may be noticeable at surgery.

### **11.6. Safety Monitoring Committee**

The Oxford University Hospitals Trust Trials Safety Group (TSG) will conduct a review of all SAEs/SADEs for the trial reported during the quarter and cumulatively. The aims of this committee include:

- To pick up any trends, such as increases in un/expected events, and take appropriate action
- To seek additional advice or information from investigators where required
- To evaluate the risk of the trial continuing and take appropriate action where necessary

## **12. STATISTICS**

### **12.1. Description of Statistical Methods**

All data will be stored in an Excel worksheet and analysed using Excel and R.

Frequency of event (adverse, hypersensitivity or complication) will equate to: number of adverse event/total number of recruited patients.

Frequency of tracer detection at surgery (at tumour site and in lymph nodes) will equate to: number of operations where tracer seen/ total number of operations on recruited patients.

Impact of tracer injection on subsequent surgery will be assessed by the surgeon's binary assessment as to whether surgery was more difficult than expected, and also free text comments to be analysed qualitatively.

A sentinel lymph node will be defined as the first lymph node draining the tumour and positivity defined according to the manufacturer's instructions. A "positive" node will be defined as having over 10% of the tracer activity of the site of initial submucosal injection. A "negative" node will be defined as having less than 10% of the tracer activity of the site of initial submucosal injection.

The detection rate for sentinel lymph nodes on MRI scan and Sentimag probe assessment will equate to: number of patients/specimens in whom a sentinel lymph node is identified/total number of examined patients/specimens.

MRI and Sentimag mapping will be qualitatively compared for all relevant patients/specimens (as appropriate) to establish a baseline of individual variability.

The presence and location of lymph nodes in the mesorectal specimen will be compared with the pathology findings for each patient in the ex-vivo part using correlation.

The success rate for removing the sentinel lymph node during TEM surgery will equate to: number of patients in whom the sentinel lymph node was removed/total number of patients undergoing TEM operation.

As this is a feasibility study, results will be continuously evaluated and adjustments made to the tracer dosage and timing of injection if indicated.

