## 5. OBJECTIVES AND OUTCOME MEASURES/ENDPOINTS

Objectives	Outcome Measures/Endpoints

Primary Objectives
 
Establish feasibility of identifying sentinel lymph node in rectal cancer:
 
[A] Adverse or hypersensitivity reactions after tracer injection in rectal cancer patients.
 
[B] Establish whether tracer is still present and detectable at the tumour injection site and in the lymph nodes at the time of surgery.
 
[C] Determine the impact of tracer injection on subsequent surgery (e.g. any difficulties due to discolouration or inflammation of tissue planes
	
[A] Frequency of adverse or hypersensitivity reaction.
 
[B] Frequency of tracer being detectable at the tumour injection site and in the lymph nodes at the time of surgery.
 
[C] Surgeon’s assessment of any difficulties encountered attributable to prior tracer injection

Secondary Objectives
 
[A] Correlate histopathology findings with tracer uptake in the lymph nodes.
 
[B] Radiologically evaluate the drainage pattern of tracer using a high resolution MRI, to establish a baseline for individual variation.
 
EX-VIVO part of study:
 
[C] Measure the distribution and spread of the tracer using the SentiMag hand-held probe in mesorectal specimen after rectal cancer surgery (in the pathology department). This is to establish a baseline in individual variation between specimens.
 
[D] Assess the accuracy of the SentiMag hand-held probe/ tracer in identifying "sentinel" lymph nodes. This will be determined in conjunction
	
[A] Correlation between histopathology findings and tracer uptake (determined by Sentimag probe) in the lymph nodes.
 
[B] High-resolution MRI mapping of the drainage pattern of tracer.
 
EX-VIVO part of the study:
 
[C] Mapping of the distribution of tracer in the mesorectal specimen using the SentiMag hand-held probe after rectal cancer surgery.
 
[D] Accuracy of the SentiMag hand-held probe/ tracer in identifying "sentinel" lymph nodes, determined by correlation with histopathology

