Intra-operative detection of the sentinel lymph node using the SentiMag probe and excision of the identified node (second part participants only): During rectal cancer surgery, following excision of the tumour, the surgeon will use the hand held SentiMag probe to identify the sentinel lymph node. This will then be dissected and removed for subsequent histological analysis.

Post-operative monitoring: Following surgery patients will be admitted to the colorectal ward for routine post-operative care. During this time they will be monitored and any adverse reactions or post-operative complications will be recorded. The patients’ participation in the study will cease when they are discharged from hospital.

Ex-vivo detection of the sentinel lymph node in the surgical specimen using the SentiMag probe (first part only): The SentiMag probe will be used to measure the distribution of the tracer and to identify the sentinel lymph node in the specimen removed during the standard surgical procedure. A Near InfraRed (NIR) imaging system will also be used to assess the specimen to detect the distribution of ICG as an adjunct to identifying lymph nodes.

Ex-vivo histological assessment of the surgical specimen: A colorectal pathologist will examine the tissue removed during surgery to identify all the lymph nodes present and whether or not they contain metastatic cancer deposits, according to standard practice. At the conclusion of the study the samples will be held in the cellular pathology department, in line with standard practice for diagnostic surgical specimens.

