### **8.7. Discontinuation/Withdrawal of Participants from Trial Treatment**

Each participant has the right to withdraw from the trial at any time. In addition, the Investigator may discontinue a participant from the trial at any time if the Investigator considers it necessary for any reason including:

- Pregnancy
- Ineligibility (either arising during the trial or retrospectively having been overlooked at screening)
- Significant protocol deviation
- Significant non-compliance with treatment regimen or trial requirements
- An adverse event which requires discontinuation of the device or results in inability to continue to comply with trial procedures
- Withdrawal of Consent
- Loss to follow up

No additional procedures or observations will continue to be required after the end of the study.

Withdrawal from the study will result in the exclusion of the data for that participant from analysis.

Withdrawn participants will be replaced by further recruitment to the study.

The reason for withdrawal will be recorded in the CRF.

If the participant is withdrawn due to an adverse event, the investigator will arrange for follow-up visits or telephone calls until the adverse event has resolved or stabilised.

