## 11. SAFETY REPORTING

### 11.1. Definitions

Adverse Event (AE)	Any untoward medical occurrence, unintended disease or injury or any untoward clinical signs (including an abnormal laboratory findings) in participants, users or other persons whether or not related to the investigational medical device. This includes events related to the investigational device or comparator, events related to the procedures involved (any procedure in the protocol). For users or other persons this is restricted to events related to the investigational medical device.
Adverse Device effect (ADE)	An adverse event related to the use of an investigational medical device. This definition includes any events resulting from insufficient or inadequate instructions for use, deployment, implantation, installation, or operation, or any malfunction of the investigational device. This definition also includes any event resulting from user error or form intentional misuse of the investigational device.
Serious Adverse Event (SAE)	
An adverse event that:
 
 
• Led to death
 
• Resulted in serious deterioration in the health of the subject that: 
 
○ resulted in a life-threatening illness or injury
 
○ resulted in a permanent impairment of a body structure or a body function
 
○ required in-patient care or prolongation of hospitalisation
 
○ resulted in medical or surgical intervention to prevent life-threatening illness or injury or permanent impairment to a body structure or a body function.
 
 
 
 
This includes device deficiencies that might have led to a serious adverse event if:
 
 
a) suitable action had not been taken or
 

	
b) intervention had not been made or
 
c) circumstances had been less fortunate.
 
These are handled under the SAE reporting system.
 
Planned hospitalisation for a pre-existing condition, or a procedure required by the trial protocol, without serious deterioration in health, is not considered a serious adverse event.

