### **11.3. Procedures for Recording Adverse Events**

All adverse events (including ADEs) and device deficiencies occurring during the course of the study will be recorded on the CRF whether or not attributed to the trial device. The information recorded will include but not be limited to:

- A description of the event
- The dates of the onset and resolution
- Action taken
- Outcome
- Assessment of relatedness to the device
- Whether the AE is serious or not
- Whether the AE arises from device deficiency
- Whether the AE arises from user error

The severity of events will be assessed on the following scale: 1 = mild, 2 = moderate, 3 = severe.

AEs/ADEs considered related to the device as judged by a medically qualified investigator or the Sponsor will be followed either until resolution, or the event is considered stable.

It will be left to the Investigator's clinical judgment to decide whether or not an AE/ADE is of sufficient severity to require the participant's removal from treatment. A participant may also voluntarily withdraw from treatment due to what he or she perceives as an intolerable AE/ADE. If either of these occurs, the participant must undergo an end of trial assessment and be given appropriate care under medical supervision until symptoms cease, or the condition becomes stable.

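### Section 8.7 drops withdrawn patients whom Section 12.6 keeps, so a patient withdrawn for a tracer reaction could disappear from primary endpoint A

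*Combined protocol and SAP*

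**What the plan says.** All references are to the combined protocol and SAP.

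- **Objective.** Section 5 gives the first primary objective as "A] Adverse or hypersensitivity reactions after tracer injection in rectal cancer patients". The matching outcome is the frequency of such reactions, with no unit stated.
- **Formula.** Section 12.1: "Frequency of event (adverse, hypersensitivity or complication) will equate to: number of adverse event/total number of recruited patients".
- **Withdrawal rule.** Section 8.7: "Withdrawal from the study will result in the exclusion of the data for that participant from analysis". It adds that withdrawn participants are replaced by further recruitment. An adverse event is among its listed reasons for discontinuing a participant, and it requires follow-up of anyone withdrawn for that reason.
- **Analysis set.** Section 12.6 puts every patient who was injected with tracer into the analysis and makes no exception for withdrawal.
- **Event data.** Section 11.1 defines an adverse event as an untoward occurrence "whether or not related to the investigational medical device". Section 11.3 puts all of these on the CRF, each with an "Assessment of relatedness to the device" on the four-level scale of Section 11.2. During the post-operative stay, Section 8 says that "any adverse reactions or post-operative complications will be recorded".

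**The concern.** The tracer is given once, and the first thing the study sets out to measure is whether patients react to it. A patient who reacts badly enough to be withdrawn is the most informative patient for that endpoint. Under Section 8.7 that patient leaves the numerator and a replacement takes the place in the denominator. Under Section 12.6 the patient stays in both. The exclusion depends on the outcome, so its effect on the numerator can only be downwards.

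The study is single-arm, so no comparator would reveal the loss. Section 12.7 marks the reporting of deviations from the statistical plan as not applicable, so an analyst could choose either rule without recording the choice.

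The formula in Section 12.1 adds a smaller ambiguity. It counts events but divides by patients, and its denominator is recruited patients where Section 12.6 speaks of injected ones.

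**Working it through.** **Inputs.** Section 12.2 gives 20 ex-vivo and 20 in-vivo patients. 20 + 20 = 40, which matches the planned sample size in the synopsis. There is no alpha, power, effect size or precision target, so 40 can be reproduced only as a sum. The documents give no reaction or withdrawal counts. Those below are assumptions.

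**Withdrawal conflict.** Let r be the number of injected patients who react and w the number of those who are withdrawn and replaced to restore 40.

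- Section 8.7: (r − w)/40
- Section 12.6: r/(40 + w)

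Exact (Clopper-Pearson) 95% limits for x out of n are the 2.5% point of Beta(x, n − x + 1) and the 97.5% point of Beta(x + 1, n − x). The lower limit is 0 when x = 0.

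| Assumed r, w | Under 8.7 | Under 12.6 |
|---|---|---|
| 1, 0 | 1/40 = 2.5% (0.1 to 13.2) | 1/40 = 2.5% (0.1 to 13.2) |
| 1, 1 | 0/40 = 0% (0 to 8.8) | 1/41 = 2.4% (0.1 to 12.9) |
| 2, 1 | 1/40 = 2.5% (0.1 to 13.2) | 2/41 = 4.9% (0.6 to 16.5) |
| 2, 2 | 0/40 = 0% (0 to 8.8) | 2/42 = 4.8% (0.6 to 16.2) |
| 4, 2 | 2/40 = 5.0% (0.6 to 16.9) | 4/42 = 9.5% (2.7 to 22.6) |

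The first row shows that a reactor who continues to surgery counts either way. The rules diverge only through patients withdrawn after injection. If those withdrawn are non-reactors, the numerator is unchanged and only the denominator moves: with one reactor who stays and one non-reactor withdrawn, 1/40 = 2.5% against 1/41 = 2.4%.

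**Unit of the 12.1 formula.** Suppose 24 of 40 patients had an adverse event of any cause, with two events each. The formula gives 24 × 2/40 = 48/40 = 1.20, while the proportion of patients affected is 24/40 = 60%. A ratio that can exceed 1 is not a proportion and has no binomial interval. The other rates in Section 12.1 match their units: operations over operations, and patients or specimens over the same.

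**Denominator.** Recruited and injected patients differ only if someone consents but is not injected. Consent and injection both take place at the endoscopy visit (Section 8.6), so the gap should be small. The two sections still name different sets.

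**The case against.** **Safety oversight is intact.** Section 8.7 itself requires follow-up of participants withdrawn for an adverse event. Section 12.4 makes any serious event a prompt for review of the study, and Section 11.6 has serious events reviewed quarterly and cumulatively. This stands: the gap is in the tabulated endpoint and not in safety reporting.

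**The conflict may never arise.** Section 11.5 calls expected reactions uncommon, and with a single injection a reactor may simply continue to surgery. This also stands. It limits the likely size, but the two rules still contradict each other, and Section 8.7 expressly foresees withdrawal for an adverse event.

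**The 12.1 wording may be loose.** It could be meant as patients with an event. That is possible, but nothing in Section 12 says so.

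A reader might also infer four stronger points that the documents do not support:

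- *One reaction could be reported as several events.* Section 11.5 speaks of a "hypersensitivity reaction such as rash, itching, dizziness and lightheadedness", which describes one reaction with example signs. Nothing says that each sign would be recorded as a separate event, so no inflated percentage should be derived from that list.
- *Surgical complications will swamp the tracer figure.* Section 12.1 can be read as one formula applied to three event types in turn. What is missing is a relatedness cut-off. The documents give no complication rates from which to size its effect, and all-cause counting would overstate harm and not hide it.
- *Section 12.5 also contradicts 8.7.* Its commitment to use all available data can mean the data left after the 8.7 exclusions.
- *Section 11.3 widens the exclusion.* It says "A participant may also voluntarily withdraw from treatment due to what he or she perceives as an intolerable AE/ADE". That is withdrawal from treatment, whereas the 8.7 exclusion is triggered by withdrawal from the study.

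**Conclusion.** Sections 8.7 and 12.6 contradict each other for any patient withdrawn after injection, and following 8.7 would bias primary endpoint A towards zero. With one reactor withdrawn and replaced the reported figure is 0% (0 to 8.8%) or 2.4% (0.1 to 12.9%). With two it is 0% (0 to 8.8%) or 4.8% (0.6 to 16.2%). These sizes rest on assumed counts, on replacement back to 40, and on no other patient reacting. The intervals overlap heavily, but reporting no reactions and reporting one or two are different safety statements.

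The unit and denominator in Section 12.1 are secondary faults of definition. The CRF already holds what a sound definition needs, and no go/no-go rule depends on the figure. The plan should be corrected because this is its first primary endpoint, but the fault does not threaten the conduct of the study.

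**What to change.** 1. **Section 8.7.** Amend it to agree with Section 12.6. Data collected up to withdrawal from every injected patient stay in endpoint A, replacements are added without displacing them, and the number of withdrawals and the reasons are reported. This concerns the handling of data only and leaves the grounds for withdrawal untouched.
2. **Section 12.1.** Define endpoint A as injected patients with at least one event, divided by all injected patients, with an exact 95% CI. Using injected patients brings the denominator into line with Section 12.6 and with an objective about reactions after injection.
3. **Tabulation.** Give that proportion three times: for all adverse events regardless of cause, for events rated possibly or most probably related under Section 11.2, and for post-operative complications. The all-cause row is needed because a pre-operative event rated unlikely or not related would otherwise appear nowhere. It also means the result does not rest solely on a rating that Section 11.2 allows the manufacturer to make.

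The cost is wording in two sections and slightly more tabulation. Relatedness (Section 11.3) and the reason for withdrawal (Section 8.7) are already on the CRF, so there is no new data collection. The reported safety figure may be slightly less favourable.

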## **8. TRIAL PROCEDURES**

Methodology training for investigators: At the start of the study, the principal investigators will undergo methodology training and practice the use of the hand held SentiMag probe device. The chief investigator will standardize the sentinel lymph node biopsy technique during this feasibility study.

Screening and preliminary discussion of research project with potential participant: During the standard pre-operative clinic visit patients who have been identified as potential participants will be screened and informed about the study by a clinician or colorectal specialist nurse. They will have an opportunity to ask questions and will be provided with an information sheet.

Informed consent: In the endoscopy unit a clinician will discuss the study further and take consent if the patient is willing to proceed. A letter will be sent to the participant's GP informing them of the study.

Endoscopic injection of tracer and post-injection monitoring: The magnetic tracer will be injected approximately 5 days before surgery during endoscopic assessment of the tumour. The rectal tumour

will be visualized by endoscopy, as per standard clinical practice. Up to 2ml tracer solution will be infiltrated systematically (in 4 quadrants) into the submucosa around the rectal tumour. After the procedure, patients will be monitored for 1 hour to ensure no hypersensitivity or adverse reactions occur and provided with a contact telephone number in case of any delayed reaction or side-effects on discharge.

MRI scan of pelvis: On the same day as the endoscopy unit visit or the day of surgery, patients will undergo an MRI scan of the pelvis. This will be done 2-3 hours after the endoscopic injection of tracer or on the day of surgery.

Rectal cancer surgery: Patients will undergo rectal cancer surgery according to their clinical indication. During surgery for the “ex-vivo” group, indocyanine green dye (ICG) will be injected near the tumour. At the conclusion of surgery the surgeon will make an assessment as to whether the tracer injection affected surgery, for example by causing inflammation in the tissue planes.

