**11.2. Causality**

The relationship of each adverse event to the trial device may be determined by the manufacturer and/or a medically qualified Investigator according to the following definitions:

**Not related:** The event is clearly related to other factors such as the patients/participants clinical condition, therapeutic intervention, concomitant medication.

**Unlikely:** The event is probably produced by other factors such as the patients/participants clinical condition, therapeutic intervention, concomitant medication and does not follow a known response pattern to the device

**Possibly:** The event follows a reasonable temporal relationship from the time of placement/administration and/or follows a known response pattern to the device but could have been caused by other factors such as the patients/participants clinical condition, therapeutic intervention, concomitant medication.

**Most probable:** The event follows a reasonable temporal relationship from the time of placement/administration and/or follows a known response pattern to the device and could not have been caused by other factors such as the patients/participants clinical condition, therapeutic intervention, concomitant medication. Further the event immediately follows the administration/placement of the device and improves on stopping or removing the device.

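### The section 12.1 formula for primary endpoint A is an all-cause ratio of events to patients and does not use the relatedness rating already on the CRF

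*Combined protocol and SAP*

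**What the plan says.** Section 5 (repeated in the synopsis) gives primary objective A as "Adverse or hypersensitivity reactions after tracer injection in rectal cancer patients" and its outcome measure as "Frequency of adverse or hypersensitivity reaction". The only formula for it is in section 12.1: "Frequency of event (adverse, hypersensitivity or complication) will equate to: number of adverse event/total number of recruited patients".

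The safety section sets out what an adverse event is and what is collected:

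- Section 11.1 defines an adverse event as an untoward occurrence "whether or not related to the investigational medical device". It separately defines an adverse device effect, which is limited to events related to the device.
- Section 11.3 says that all adverse events "will be recorded on the CRF whether or not attributed to the trial device". The fields listed include onset and resolution dates, seriousness, and "Assessment of relatedness to the device".
- Section 11.2 gives a four-level scale (not related, unlikely, possibly, most probable) and says: "The relationship of each adverse event to the trial device may be determined by the manufacturer and/or a medically qualified Investigator".

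Sections 8 and 8.6 add that post-operative complications are recorded up to discharge. Section 8 also says that during surgery in the ex-vivo group "indocyanine green dye (ICG) will be injected near the tumour". Section 12.6 analyses everyone who received the tracer, whereas section 8.7 drops the data of anyone who withdraws and replaces that participant.

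**The concern.** The endpoint is about reactions to the tracer, but the formula counts adverse events of any cause. Patients are followed through rectal cancer surgery to discharge, so events that have nothing to do with the tracer are to be expected. The protocol defines a related-event category, grades relatedness and puts it on the CRF, yet the analysis text uses none of this.

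The unit is a second difficulty. Events are divided by patients, and nothing says that each patient counts once. Other ratios in 12.1 match their units, for example patients over patients for sentinel node removal at TEM.

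What is at stake is how informative the first-listed primary outcome will be. Section 4 says that a clinical trial of sentinel node biopsy is intended next. That trial will need to know how many patients reacted to the tracer, and the formula as written does not tell it.

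**Working it through.** **Inputs.** Planned size is 20 ex-vivo + 20 in-vivo = 40 (section 12.2 and synopsis). The formula is in 12.1. The plan states no expected rate, threshold or interval for endpoint A, so there is no figure of its own to reproduce. All event counts below are assumptions chosen to show the range.

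**Formulas.**
- Plan: R = adverse events / recruited patients.
- Comparison: P = patients with at least one tracer-related reaction / injected patients, with exact (Clopper-Pearson) 95% limits. The lower limit is the 0.025 quantile of Beta(x, n − x + 1) and the upper limit is the 0.975 quantile of Beta(x + 1, n − x).

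**Step 1: relatedness.** The bracket in 12.1 names three event types and can be read as one pooled ratio or as three separate ones. Take one tracer reaction plus u unrelated events in 40 patients. On the pooled reading, u includes complications. On the separate reading, which is the more natural one, u for the adverse ratio covers only unrelated events classed as adverse events rather than complications, so it may be small.

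| Unrelated events u | R | P |
|---|---|---|
| 0 | 1/40 = 2.5% | 1/40 = 2.5% |
| 4 | 5/40 = 12.5% | 2.5% |
| 8 | 9/40 = 22.5% | 2.5% |
| 16 | 17/40 = 42.5% | 2.5% |

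The exact interval for 1/40 is 0.1% to 13.2%. Separating the three types lowers u but does not bring relatedness into the formula.

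**Step 2: unit.** Section 11.5 lists rash, itching, dizziness and lightheadedness as expected hypersensitivity signs. If one reacting patient has three of them recorded as three events, R = 3/40 = 7.5% against P = 1/40 = 2.5%. This arises even when hypersensitivity is tabulated alone. For all-cause events, 8 events in 6 patients give 8/40 = 20%, against 6/40 = 15% of patients (5.7% to 29.8%).

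**Step 3: ICG.** The tracer is injected about 5 days before surgery and ICG during surgery, in ex-vivo patients only (section 8). A reaction before surgery therefore cannot be due to ICG, and onset dates are recorded (11.3). Confusion is possible only for reactions at or after surgery in 20 of the 40 patients, and known iodine intolerance is already excluded (7.3). If one such ICG reaction were counted beside one tracer reaction, hypersensitivity would read 2/40 = 5.0% rather than 2.5%. With none, the two figures agree.

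**Step 4: denominator.** Suppose the one reacting patient is withdrawn for that event and replaced. Then 41 patients were injected. Section 12.6 gives 1/41 = 2.4%. Section 8.7 gives 0/40 = 0% (0% to 8.8%), and the reaction disappears from the analysis.

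**The case against.** The endpoint says frequency and never promises a proportion of patients. Events per patient is a legitimate frequency, and the fact that it can exceed 1 is not in itself an error. This stands: a reader might infer that 12.1 fails to deliver a proportion that the protocol committed to, and the documents do not support that. What remains is that an all-cause frequency does not describe reactions to the tracer, which is what objective A asks about.

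The numerator wording is loose and may have meant patients with an event, in keeping with the other ratios in 12.1. That is possible, but no text says so, and it would settle only the unit.

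A reader might also infer that surgical complications will swamp the endpoint. That depends on the pooled reading, which is the less natural one because 12.1 names three event types and complications are recorded as their own item. The larger rows in Step 1 show what the formula permits, not what is likely.

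Nor do the documents support a general contamination by ICG, given the timing set out in Step 3.

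Finally, this is a descriptive 40-patient feasibility study with no significance level (12.3). Attribution is collected, so no data are lost. That also stands, and it limits the importance of the point.

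**Conclusion.** The point holds as a mismatch between endpoint and formula. Followed literally, 12.1 yields an all-cause ratio of events to patients, whereas endpoint A concerns reactions after tracer injection. Unrelated peri-operative events can enter the adverse ratio even if the three event types are tabulated separately, and repeated events in one patient inflate any of the ratios.

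The size cannot be estimated from the documents. Under the assumed counts the gap runs from nothing to tens of percentage points, and the upper end needs many unrelated events in the same ratio.

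The consequence is modest. No decision threshold rests on endpoint A, serious events are reviewed separately (11.6, 12.4), and the CRF allows the right figure to be derived. It would be wrong to conclude that the trial cannot describe tracer safety. The plan simply does not tell the analyst to compute the figure that does so. This is a worthwhile clarification, not a flaw in the design.

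**What to change.** In section 12.1:

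1. Report endpoint A as the number and percentage of injected patients (12.6) with at least one adverse event or hypersensitivity reaction rated possibly or most probably related to the tracer, with an exact 95% interval.
2. Specify that the rating used is the medically qualified investigator's. Section 11.2 also allows the manufacturer to rate, and the manufacturer funds the devices and consumables (17.1).
3. Beside it, report all-cause adverse events and post-operative complications as patients affected, with event counts and seriousness. The reader is then not wholly dependent on the relatedness judgement.
4. For ex-vivo patients, use onset date relative to surgery to separate tracer reactions from possible ICG reactions.
5. State that injected patients who later withdraw stay in this safety analysis despite 8.7, unless they withdraw consent to the use of their data.

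The cost is a few sentences and one table, mostly from fields already on the CRF. The downsides are small: some cells will be sparse or empty, and some reactions at surgery cannot be attributed with certainty.
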